RAPID local ischemic postconditioning in acute ischemic Stroke
pAtients recei**V**Ed successful thrombectomy reperfusion (**RAPID-**
SAVE)

STATISTICAL ANALYSIS PLAN

Principal Investigator

[name], PhD

Shanghai Sixth People's Hospital Affiliated to Shanghai Jiao Tong University School
of Medicine

Clinical Trial: NCT06526429

Protocol Version 1.0

Oct 14, 2024

BOIN12 Study Design and Statistical Analysis Plan

2 This study employed the Bayesian optimal interval phase I/II (BOIN12) trial design¹
3 find the optimal biological dose (OBD). The BOIN12 design used utility to quantify
4 the desirability of a dose in terms of toxicity-efficacy trade off and adaptively
5 allocated patients to the dose that has the highest estimated desirability. The utilities
6 ascribed to each possible efficacy-toxicity outcome were as follows: (No Toxicity,
7 Efficacy) = 100; (Toxicity, Efficacy) = 60; (No Toxicity, No Efficacy) = 40; and
8 (Toxicity, No Efficacy) = 0. A higher value indicated a more desirable outcome (0
9 and 100 present the least and most desirable outcome, respectively).

10 Let u_1, \dots, u_4 denote these utilities. Given a dose j , let p_1, \dots, p_4 denote the
 11 corresponding probabilities of observing each of the possible toxicity-efficacy
 12 outcomes. Then, the mean utility of dose j is

$$uj=p1u1+p2u2+p3u3+p4u4.$$

14 A higher value of uj indicated a higher desirability of dose j in terms of risk-benefit
15 tradeoff. To safeguard patients from toxic and/or futile doses, two dose acceptability
16 criteria were used by BOIN12 to decide which doses might be used to treat patients.
17 A dose was deemed as admissible and eligible for treating patients if it satisfied the
18 following safety and efficacy criteria.

(Safety) $\Pr(\pi T > 0.15 \mid \text{data}) < 0.95$,

(Efficacy) $\Pr(\pi E < 0.6 \mid \text{data}) < 0.9$.

21 where πT and πE were the true DLT rate and efficacy rate, respectively. These two
22 conditions ensured that the admissible dose could not be overly toxic or futile. Doses
23 that were not admissible would be eliminated from the trial. If a dose was eliminated
24 due to toxicity, all doses higher than that dose would also be eliminated. The
25 objective was to identify the OBD, defined as the dose that was admissible and had
26 the highest desirability.

RAPID-SAVE Trial SAP

27 We planned to enrol a maximum number of 60 patients with a cohort size of 5. When
28 the current dose's observed toxicity rate fell within the stay interval of BOIN, we
29 would stop exploring higher doses if its number of patients $\geq N^*$, where $N^* = 5$. The
30 BOIN12 design is depicted in Supplemental Figure 1 and it was implemented
31 according to the following 3 steps via the BOIN12 shiny app².

32 1. Treat the first cohort at dose level 3.
33 2. Suppose that the current dose level is j , choose one of the following three
34 cases to determine the dose for treating the next cohort of patients:

35 **Case A:** determine the desirability of dose levels $j-1$, j , and $j+1$ using the
36 rank-based desirability score (RDS) table (Table 1), and choose the one that
37 has the highest desirability to treat the next cohort. If the RDS of all three
38 doses are “E,” stop the trial and no dose should be selected. In the case that
39 dose level $j-1$ (or $j+1$) does not exist, then apply the above rule to dose
40 levels j and $j+1$ (or j and $j-1$).

41 **Case B:** determine the desirability of dose levels j and $j-1$ using the RDS
42 table (Table 1), and choose the one that has the higher desirability to treat the
43 next cohort. If the RDS of the two doses are “E,” stop the trial and no dose
44 should be selected. If the current dose level j is the lowest dose, treat the next
45 cohort of patients at the lowest dose unless the RDS of the lowest dose is “E,”
46 at which point terminate the trial.

47 **Case C:** determine the desirability of dose levels j and $j-1$ using the RDS
48 table (Table 1).

49

- 50 ○ If the current dose level j is the lowest dose, treat the new patients at
51 the lowest dose unless the RDS of the lowest dose is “E,” at which
 point terminate the trial.

52 ○ If the current dose level j is not the lowest dose and the RDS of dose
53 level $j-1$ is not “E,” de-escalate the dose to level $j-1$ to treat the next
54 cohort of patients.

55 If the current dose level j is not the lowest dose and the RDS of dose
56 level $j-1$ is “E,” stay at the current dose level j to treat the next cohort of
57 patients unless the RDS of dose level j is “E,” at which point terminate the
58 trial. In the event of **Case A** or **Case B**, to prevent getting stuck in a local
59 dose, an extra dose exploration rule is implemented to escalate to the next
60 higher untried dose if the following two conditions are met:

61 ○ The number of patients treated at the current dose is ≥ 15 .
62 ○ The next higher dose is not eliminated and has never been used for
63 treating patients.

64 3. Repeat step 2 until the maximum sample size of 60 is reached or if the number
65 of patients treated on any dose reaches 20. Then, use the isotonic estimation
66 method described in Lin et al.¹ to select the OBD as the dose that is admissible
67 and that has the highest estimated utility.

[figure not shown]

Figure 1. Flowchart for trial conduct using the BOIN12 design, where $N^*=5$,

and $(\lambda_e, \lambda_d) = (0.118, 0.179)$.

eTable 1. Rank-based desirability score (RDS) table for the BON12 design, where “E” means elimination. A larger value of RDS means higher desirability, and any value of RDS is deemed higher than “E”. #Pts denotes the number of evaluable patients treated at current dose; #Tox denotes the number of evaluable patients who experience toxicity; #Eff denotes the number of evaluable patients who experience efficacy.

#Pts	#Tox	#Eff	RDS												
0	0	0	262	15	0	7	96	15	4	9	61	20	2	19	528
5	0	<= 1	E	15	0	8	159	15	4	10	115	20	2	20	556
5	0	2	169	15	0	9	232	15	4	11	183	20	3	<= 9	E
5	0	3	268	15	0	10	297	15	4	12	256	20	3	10	19
5	0	4	377	15	0	11	366	15	4	13	321	20	3	11	47
5	0	5	483	15	0	12	435	15	4	14	389	20	3	12	90

RAPID-SAVE Trial SAP

#Pts	#Tox	#Eff	RDS												
5	1	<= 1	E	15	0	13	497	15	4	15	457	20	3	13	147
5	1	2	101	15	0	14	542	15	>= 5	Any	E	20	3	14	213
5	1	3	199	15	0	15	565	20	0	<= 9	E	20	3	15	264
5	1	4	308	15	1	<= 6	E	20	0	10	90	20	3	16	328
5	1	5	413	15	1	7	61	20	0	11	147	20	3	17	391
5	>= 2	Any	E	15	1	8	115	20	0	12	213	20	3	18	448
10	0	<= 4	E	15	1	9	183	20	0	13	264	20	3	19	501
10	0	5	172	15	1	10	256	20	0	14	328	20	3	20	539

RAPID-SAVE Trial SAP

#Pts	#Tox	#Eff	RDS												
10	0	6	250	15	1	11	321	20	0	15	391	20	4	<= 9	E
10	0	7	330	15	1	12	389	20	0	16	448	20	4	10	8
10	0	8	414	15	1	13	457	20	0	17	501	20	4	11	27
10	0	9	492	15	1	14	514	20	0	18	539	20	4	12	59
10	0	10	545	15	1	15	550	20	0	19	561	20	4	13	109
10	1	<= 4	E	15	2	<= 6	E	20	0	20	571	20	4	14	170
10	1	5	117	15	2	7	31	20	1	<= 9	E	20	4	15	227
10	1	6	196	15	2	8	75	20	1	10	59	20	4	16	287

RAPID-SAVE Trial SAP

#Pts	#Tox	#Eff	RDS												
10	1	7	286	15	2	9	136	20	1	11	109	20	4	17	351
10	1	8	360	15	2	10	204	20	1	12	170	20	4	18	410
10	1	9	444	15	2	11	276	20	1	13	227	20	4	19	468
10	1	10	513	15	2	12	347	20	1	14	287	20	4	20	515
10	2	<= 4	E	15	2	13	412	20	1	15	351	20	5	<= 9	E
10	2	5	69	15	2	14	478	20	1	16	410	20	5	10	2
10	2	6	141	15	2	15	529	20	1	17	468	20	5	11	12
10	2	7	220	15	3	<= 6	E	20	1	18	515	20	5	12	34

RAPID-SAVE Trial SAP

#Pts	#Tox	#Eff	RDS												
10	2	8	306	15	3	7	16	20	1	19	549	20	5	13	73
10	2	9	387	15	3	8	46	20	1	20	566	20	5	14	129
10	2	10	467	15	3	9	96	20	2	<= 9	E	20	5	15	192
10	3	<= 4	E	15	3	10	159	20	2	10	34	20	5	16	243
10	3	5	37	15	3	11	232	20	2	11	73	20	5	17	312
10	3	6	94	15	3	12	297	20	2	12	129	20	5	18	371
10	3	7	172	15	3	13	366	20	2	13	192	20	5	19	430
10	3	8	250	15	3	14	435	20	2	14	243	20	5	20	488

RAPID-SAVE Trial SAP

#Pts	#Tox	#Eff	RDS	#Pts	#Tox	#Eff	RDS	#Pts	#Tox	#Eff	RDS	#Pts	#Tox	#Eff	RDS
10	3	9	330	15	3	15	497	20	2	15	312	20	\geq 6	Any	E
10	3	10	414	15	4	≤ 6	E	20	2	16	371				
10	≥ 4	Any	E	15	4	7	6	20	2	17	430				
15	0	≤ 6	E	15	4	8	23	20	2	18	488				

Reference

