65 moderate AIS^{13,14}, but this finding was not confirmed by other reports^{15,16}. The delay
66 of remote ischemic postconditioning initiation after thrombolysis can’t protect from the
67 reperfusion injury. Rapid local ischemic postconditioning (RL-IPostC) , referring to the
68 intervention promptly initiated after the onset of reperfusion that directly modulates the
69 rapid augmentation of blood flow during reperfusion, may theoretically attenuate
70 reperfusion injury. Previous reports have demonstrated neuroprotective effects in
71 animal models of cerebral ischemia¹⁷⁻²⁰, yet remain unproven in clinical practice. With
72 the widespread application of EVT for revascularization in LVO-AIS, RL-IPostC can

73 now be rapidly and conveniently implemented. Recent studies indicate that RL-IPostC
74 is feasible and well-tolerated in AIS patients undergoing EVT, suggesting it could be a
75 promising therapy to mitigate cerebral ischemia-reperfusion injury²¹⁻²³. The most
76 effective ischemic postconditioning protocol, has yet to be identified.

77 **3 STUDY OBJECTIVES**

78 To determine the safety and efficacy of RL-IPostC on LVO-AIS of successful
79 thrombectomy, and the optimal dosage of RL-IPostC.

80 **4 STUDY DESIGN AND MANAGEMENT OVERVIEW**

81 **4.1 Study design overview**

82 The study is an investigator-initiated prospective, adaptive, multicenter clinical trial. It
83 employs the Bayesian Optimal Interval Phase I/II (BOIN12) trial design to assess the
84 safety and determine the optimal dosage of ischemic postconditioning intervention. The
85 BOIN12 design facilitates decisions regarding dosage escalation and de-escalation by
86 simultaneously taking account of toxicity and efficacy. It quantifies the desirability of
87 a dosage in terms of toxicity-efficacy trade-off. Within the BOIN12 framework,
88 patients are adaptively assigned to the most desirable dosage, balancing optimal toxicity
89 and efficacy. The rank-based desirability score (RDS) can be pre-tabulated before the
90 trial commences using the quasi-beta-binomial model²⁴. In this trial, the following
91 toxicity-efficacy trade-off utilities are established for calculating the RDS: (No Toxicity,
92 Efficacy) = 100; (Toxicity, Efficacy) = 60; (No Toxicity, No Efficacy) = 40; (Toxicity,
93 No Efficacy) = 0. The RDS table will be detailed in statistical analysis plan.

94 Stopping criteria are implemented to prevent the allocation of patients to dosage that is

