95 severely toxic or ineffective. BOIN12 utilizes two dosage-acceptability criteria to
96 determine which dosage may be administered. If the probability of a toxicity outcome
97 exceeding the upper limit of toxicity 0.15 is greater than 0.95, then dosage level and
98 higher are eliminated from the trial. Conversely, if the probability of an efficacy

99 outcome falling below the lower limit of efficacy 0.60 is more than 0.90, then dosage
100 level is removed from consideration. The dosage that is both admissible and has the
101 highest estimated utility will be selected as the optimal dosage.

102 **4.2 Blinding**

103 Although the treatment medications are known to the patients and the treating
104 neurointerventionist, the study employs a blinded assessment. Investigators responsible
105 for follow-up neurological evaluations, as well as the independent Clinical Events
106 Committee (CEC), are kept unaware of treatment group assignment to maintain
107 objectivity. These assessors have no role in patient care.

108 **4.3 Study milestones**
109 A 16-month budget and recruitment plan have been planned; the key study milestones
are shown in the table below.

STUDY MILESTONES

Pre-enrollment study initiation	2 months
Recruitment and follow-up	9 months
Completion of follow-up	3 months
Data analysis and publication	2 months
Total duration	16 months

110 This schedule is preliminary and may be adjusted based on the progress of the study.

111 **4.4 Site recruitment**

112 Six National Comprehensive Stroke Centers will be designated as trial sites. Selection
113 will be based primarily on the following criteria: (1) prior experience in multicenter
114 clinical trials; (2) an annual volume of no fewer than 50 endovascular thrombectomy
115 procedures for AIS over the past three years; and (3) routine use of a balloon guide
116 catheter in these procedures.

117 **4.5 Site training, certification, and updates.**

118 All investigators are required to complete the following training modules and receive
119 certification:

120 ● Study procedures
121 ● Primer on the diagnosis of ischemic stroke.
122 ● Rapid-SAVE eligibility
123 ● Modified Rankin Scale score
124 ● NIHSS

125 Successful completion of the training program and approval from the local Institutional
126 Review Board (IRB) for human research will be required before a site can be certified
127 to enroll patients. Intermittent web-based meetings with the principal investigator and

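### The SAP says its two admissibility criteria rule out a futile or overly toxic dose; they only make one less likely, and naming an OBD cannot meet the efficacy aim in Protocol Section 3

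*SAP*

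**What the plan says.** The SAP's opening section gives two conditions for a dose to be admissible: Pr(πT > 0.15 | data) < 0.95 and Pr(πE < 0.6 | data) < 0.9. It then says that these "conditions ensured that the admissible dose could not be overly toxic or futile". Doses "that were not admissible would be eliminated from the trial", and elimination for toxicity also removes every higher dose.

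Protocol Section 4.1 gives the same limits in words. A dose and those above it go if the probability of toxicity "exceeding the upper limit of toxicity 0.15 is greater than 0.95, then dosage level and"; a dose goes if the probability of an efficacy "outcome falling below the lower limit of efficacy 0.60 is more than 0.90, then dosage".

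eTable 1 turns the rules into counts. A dose is eliminated for efficacy at ≤1/5, ≤4/10, ≤6/15 or ≤9/20 successes, and for toxicity at ≥2/5, ≥4/10, ≥5/15 or ≥6/20 DLTs. SAP step 3 selects the dose that is admissible "and that has the highest estimated utility".

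On objectives, Protocol Section 3 reads "To determine the safety and efficacy of RL-IPostC on LVO-AIS of successful" thrombectomy, plus the optimal dosage. Section 4.1 describes the design as meant to assess the "safety and determine the optimal dosage of ischemic postconditioning intervention", and the synopsis objective likewise names only safety and optimal dosage.

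**The concern.** Each criterion asks whether the data strongly show that a dose is bad. Neither asks for evidence that it is good. A dose can therefore be more likely than not on the wrong side of the plan's own limit and still be admissible. The SAP sentence claims the opposite.

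Two conclusions are at stake. First, a retained dose could be reported as established to be neither futile nor overly toxic. Second, Section 3 invites the OBD to be read as an answer on efficacy, although the plan has no control arm, no reference rate, no interval or posterior statement for the OBD's efficacy, and no operating characteristics.

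**Working it through.** **Reproducing the plan's figures.** Use a Beta(1,1) prior (my assumption; the documents state none). With x events in n patients, the posterior is Beta(1+x, 1+n−x).
- Eliminating when Pr(πE < 0.6) > 0.90 gives ≤1, 4, 6, 9 at n = 5, 10, 15, 20.
- Eliminating when Pr(πT > 0.15) > 0.95 gives ≥2, 4, 5, 6.
- All eight limits match eTable 1. A Beta(0.5,0.5) prior does not (it gives ≥3 DLTs at n = 5).
- The BOIN boundaries with 0.6 × 0.15 and 1.4 × 0.15 come to 0.1178 and 0.1787, matching the SAP's 0.118 and 0.179.

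**What the limits keep.**
- 10/20 successes: Pr(πE < 0.6) = 0.826, below 0.90, so kept. The 95% credible interval is 0.30 to 0.70.
- 5/20 DLTs: Pr(πT > 0.15) = 0.917, below 0.95, so kept. At 6/20 it is 0.971, so eliminated.

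**Retention of one isolated dose.** Add Binomial(5, p) cohorts and drop every path that meets an elimination limit at n = 5, 10, 15 or 20. First look at true efficacy 0.50: 1 − (1+5)/32 = 0.8125. First look at true DLT rate 0.20: 0.8^5 + 5 × 0.2 × 0.8^4 = 0.328 + 0.410 = 0.737. Continuing:

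| Rule alone | True rate | n=5 | n=10 | n=15 | n=20 |
|---|---|---|---|---|---|
| Efficacy | 0.30 | 0.47 | 0.14 | 0.08 | 0.03 |
| Efficacy | 0.40 | 0.66 | 0.34 | 0.27 | 0.18 |
| Efficacy | 0.50 | 0.81 | 0.59 | 0.55 | 0.46 |
| Efficacy | 0.60 | 0.91 | 0.81 | 0.79 | 0.76 |
| Toxicity | 0.20 | 0.74 | 0.71 | 0.67 | 0.63 |
| Toxicity | 0.25 | 0.63 | 0.59 | 0.52 | 0.45 |

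Applying both rules at true efficacy 0.50, with independent outcomes, gives 0.45, 0.42 and 0.36 at assumed DLT rates of 0.05, 0.10 and 0.15.

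**Whole trial.** I simulated SAP steps 1 to 3 with 10,000 trials per scenario (Monte Carlo standard error at most 0.5 points). An all-E stop ("stop the trial and no dose should be selected") counts as no OBD. Assumptions:
- the true rates, with efficacy and toxicity independent;
- Case A/B/C triggers taken from λe and λd, because the flowchart is not shown;
- a utility cut-off of 0.85 on the 0–1 scale for the desirability score, which put 29 sampled eTable 1 entries in the right order;
- isotonic estimation applied to the DLT rates at selection;
- ties broken at random.

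Results:
- All six doses at efficacy 0.50, DLT 0.05: an OBD is named in about 80% of trials.
- All six at DLT 0.20, above the limit: an OBD is named in about 60% (efficacy 0.60) to 75% (efficacy 0.80). At DLT 0.25, about 41% to 54%.
- One dose at 0.80 and five at 0.50, DLT 0.05: a 0.50 dose is named in about 13% of trials if level 3 is the good dose, and about 43% if level 4 is.
- Mean observed efficacy at the OBD (flat scenarios, DLT 0.05): 0.62 when the truth is 0.50, and 0.72 when it is 0.63.
- Mean observed DLT rate at the OBD: 0.15 at true 0.20, 0.17 at true 0.25, 0.12 to 0.13 at true 0.15, and about 0.05 at true 0.05.
- The lower 95% efficacy limit lies above the truth in 7.3% of trials with an OBD at true 0.50, 4.6% at 0.60, 6.7% at 0.63 and 2.0% at 0.80 (DLT 0.05; nominal 2.5%).

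**The case against.** A lenient futility and toxicity screen is a legitimate feature of dose finding. The SAP prints both inequalities just before the disputed sentence and every retained count in eTable 1, so nobody applying the design is misled about allocation. The screen also works against clearly poor doses: retention through 20 patients is 0.18 at true efficacy 0.40 and 0.03 at 0.30. All of this stands, and it is why the algorithm need not change. It does not make the sentence true.

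The retention figures are conditional on one dose receiving 20 patients. With all doses at 0.50 and DLT 0.05, a given level reached 20 in only about 8–22% of trials. The toxicity figures also ignore removal through elimination of a lower dose: with DLT 0.20 at every level and efficacy elimination switched off, level 3 ended toxicity-admissible in about 49% of trials, against 63% in isolation. The flat scenarios leave out the design's main task, choosing between doses that differ. These points stand, and the conditions must accompany the numbers.

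A reader might infer that the 0.46 is the reason an OBD cannot show efficacy. The documents do not support that link. The obstacle is the lack of a comparator or reference rate, and a perfect screen at 0.60 would not remove it. Nor do the documents say that an OBD demonstrates efficacy; only the Section 3 aim points that way. The Background figure of up to 37% with infarct growth cannot serve as a reference: it comes without a growth threshold or time window, so 63% without growth is only an inference.

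**Conclusion.** The concern holds as an overstated property and an inconsistent objective; severity is minor to moderate. The criteria lower the chance of keeping a futile or overly toxic dose but do not exclude it. In isolation and through 20 patients, retention is 0.46 at true efficacy 0.50, 0.76 at 0.60, 0.63 at a true DLT rate of 0.20 and 0.45 at 0.25, each under one rule alone. These figures rest on eTable 1's limits and the assumed true rates; the trial-level percentages also rest on the simulation assumptions listed.

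Section 3 conflicts with the synopsis and Section 4.1, and its efficacy aim cannot be met by naming an OBD.

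A reader might also infer that observed rates at the OBD are always flattering. That is too strong. Efficacy is overstated in the flat scenarios examined, but the DLT rate is understated only when true rates are near or above 0.15; at 0.05 it is essentially unbiased.

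**What to change.** (a) Replace the SAP sentence with: *These conditions reduce, but do not exclude, the chance of retaining a futile or overly toxic dose.* Follow it with the isolated-dose retention figures and their conditions: one dose given 20 patients, checked after each cohort of 5, one rule at a time, ignoring removal through a lower dose. Add an operating-characteristics table with flat scenarios (for example all doses at efficacy 0.50 and DLT 0.05) and scenarios where doses differ (for example one dose at 0.80, the rest at 0.50). Label the true rates, case triggers, utility cut-off of 0.85 and isotonic step as assumptions unless the sponsor can confirm them.

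(b) Align Section 3 with the synopsis and Section 4.1.

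(c) Add to SAP step 3: *Selection of an OBD is not evidence of efficacy over thrombectomy alone. Observed efficacy and DLT rates at the OBD are reported with 95% credible intervals (Beta(1,1) prior), noting that selection tends to overstate efficacy and, when true DLT rates are near or above the 0.15 limit, to understate the DLT rate.*

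The cost is two SAP wording changes, one protocol sentence and one simulation table. No patients are added, and allocation, elimination and OBD selection are unchanged. The downside is a less favourable statement about the design.

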128 key staff will be scheduled to address problems. A video of RL-IPostC conduction with
129 BGC is recorded for interventionist training, reviewed in detail in the training modules.
130 Case studies illustrating potential problems in adhering to the study protocol and
131 blinding will be discussed. This will serve as a guide for training clinical site personnel
132 and will be updated periodically throughout the study as needed.

133 An Executive Committee will be organized and periodically distribute a set of
134 frequently asked questions and answers to the participating centers. Any queries
135 regarding the study procedures during the study period will be addressed by the
136 executive committee through calls or messages through Wechat.

137 4.6 Outcomes

138 The safety outcomes within 7 days, which are categorized as dosage-limiting toxicities
139 (DLTs), including the following criteria: 1) Malignant MCA infarction, defined by a
140 midline shift of ≥ 5 mm at the level of septum pellucidum, anisocoria due to herniation,
141 or death resulting from herniation; 2) Complications associated with ischemic
142 postconditioning intervention that necessitate treatment, including distal vascular
143 embolism, local arterial dissection and vascular spasm at the intervention site of the
144 ICA; 3) Serious adverse events (SAEs) that are causally linked to the intervention.

145 The efficacy outcome is defined by the reduction in infarction growth, measured as an
146 infarction growth < 10 mL from baseline to 72 hours post-intervention. Infarction
147 volume will be evaluated using automate software analysis, which assesses baseline

148 CTP defined by relative cerebral blood flow (rCBF) $<30\%$ and 72-hour diffusion-
149 weighted imaging (DWI) or CT hypodensity volume.

150 5 PARTICIPANT SELECTION

151 All subjects will undergo a neurological and clinical assessment, routine laboratory
152 blood test and baseline brain imaging. All these materials will be collected and
153 screened by site physician. This includes standard of care use of non-contrast CT/ CT
154 angiography/ CT perfusion. In order to track the potential for enrollment, screening
155 log is required. Potential embolic LVO-AIS within 24 h of symptom onset ready for
156 thrombectomy will be screened and signed informed consent if patients meet the
157 inclusion and exclusion criteria except the item 9 and 10 of inclusion criteria. Before

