198 warrant withdrawal; such cases must be adjudicated by the Clinical Events Committee
199 (CEC) to determine if they constitute an RL-IPostC-related adverse event. All
200 withdrawal cases will be documented in the case report form (CRF) and preserved for
201 audit. Withdrawn patients will be excluded from the efficacy analysis.

202 5.3 Criteria for drop out

203 All patients enrolled in the trial will be retained until the completion of the follow-
204 up. Subjects may request the withdrawal of informed consent and withdrawal from
205 this study at any time without any reason, and their medical rights will not be affected.
206 The investigator may also consider it medically necessary for the subject to
207 discontinue the study. For subjects who withdraw from the study, their reason for
208 withdrawal will be recorded, and the mRS score will be completed as far as possible
209 before withdrawal.

210 5.4 Criteria for discontinuation of clinical studies

211 This study will provide an optimal balance between safety and efficacy according to
212 pre-designed acceptable criteria, and the dosage will be abandoned or stopped once
213 unacceptable safety and efficacy criteria are met.

214 6 TREATMENTS

215 RL-IPostC procedure is administered immediately (within 5 minutes) following
216 revascularization. A balloon guiding catheter (BGC) is positioned at the ipsilateral C1
217 segment of ICA and is inflated and deflated to temporary stop antegrade blood flow.
218 This study examines six dosages levels, with the initial dosage set at Dosage
219 3(2min/2min, 4 cycles). The dosing schedule is as follows:

220 ① Dosage 1 (RL-IPostC 15/15, 5cycles): The intervention dosage consist of 15
221 seconds of occlusion followed by 15 seconds of reperfusion, repeated for 5 cycles.
222 ② Dosage 2 (RL-IPostC 60/60, 4 cycles): The intervention dosage consist of 60
223 seconds of occlusion followed by 60 seconds of reperfusion, repeated for 4 cycles.
224 ③ Dosage 3 (RL-IPostC 120/120, 4 cycles): The intervention dosage consist of 120
225 seconds of occlusion followed by 120 seconds of reperfusion, repeated for 4 cycles.
226 ④ Dosage 4 (RL-IPostC 180/180, 4 cycles): The intervention dosage consist of 180
227 seconds of occlusion followed by 180 seconds of reperfusion, repeated for 4 cycles.
228 ⑤ Dosage 5 (RL-IPostC 240/240, 4 cycles): The intervention dosage consist of 240
229 seconds of occlusion followed by 240 seconds of reperfusion, repeated for 4 cycles.

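### The toxicity elimination rule has no within-cohort trigger, so up to 3 patients in a dosage's first cohort may be treated after eTable 1 has already fixed its elimination

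*SAP*

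**What the plan says.** **Criterion.** Protocol 4.1 removes a dosage, and all above it, when the probability of toxicity "exceeding the upper limit of toxicity 0.15 is greater than 0.95, then dosage level and" higher are dropped. The SAP states the same limit and cutoff, and makes admissibility a condition for treating patients at a dose.

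**Timing in the Protocol.** Section 5.4 refers to "pre-designed acceptable criteria, and the dosage will be abandoned or stopped once" the unacceptable criteria are met. It names no schedule of looks.

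**Timing in the SAP.** "We planned to enrol a maximum number of 60 patients with a cohort size of 5". Step 2 applies the RDS table when choosing among "cases to determine the dose for treating the next cohort of patients". In eTable 1, "Pts denotes the number of evaluable patients treated at current dose", and the rows exist only at 0, 5, 10, 15 and 20. The toxicity entries that give E at any efficacy count are 2 or more in 5, 4 or more in 10, 5 or more in 15, and 6 or more in 20.

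**Oversight.** Under Protocol 7.3 and 7.4 the CEC judges relatedness, and SAEs are reported to the investigator and the Ethics Committee within 24 hours. Under 8.3 the DSMB meets as needed, reviews SAEs and advises on dosage and on stopping. Under 9.1 the Ethics Committee may ask for suspension at any time. None of these has a DLT-count trigger.

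**The concern.** A DLT count cannot fall. Once the eTable 1 count for the cohort in progress is reached, the remaining patients of that cohort cannot reverse the elimination. Treating them at that dosage exposes them to something the trial's own rule has excluded. It adds almost nothing to the decision and uses places out of the maximum of 60. The DLT definition in Protocol 4.6 includes malignant infarction and death from herniation, so the exposure is not trivial. The issue can arise in the very first cohort, which starts at level 3 of 6.

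The two documents also give different answers on timing. Protocol 5.4 and the SAP's admissibility paragraph read as immediate, while SAP step 2 acts between cohorts. A site with two DLTs in its first three patients could not tell from the plan whether the fourth patient may be treated.

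**Working it through.** **1. Reproduce the eTable 1 toxicity limits.** Protocol 4.1 says the table is fixed before the "trial commences using the quasi-beta-binomial model". The prior for the toxicity rate is not stated, so I assume Beta(1,1). With x DLTs in n patients, Pr(πT > 0.15) = 1 − BetaCDF(0.15; 1 + x, 1 + n − x). The limit is the smallest x that gives more than 0.95.

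| n | one DLT below the limit | at the limit |
|---|---|---|
| 5 | 1: 0.7765 | 2: 0.9527 |
| 10 | 3: 0.9306 | 4: 0.9841 |
| 15 | 4: 0.9209 | 5: 0.9765 |
| 20 | 5: 0.9173 | 6: 0.9713 |

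All four limits match eTable 1.

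**2. When is elimination certain in a first cohort?** It is certain at the second DLT. If the true DLT rate is p, the chance that the second DLT falls on patient k is (k − 1)p²(1 − p)^(k−2), and 5 − k patients then remain. Early certainty means k = 2, 3 or 4, leaving 3, 2 or 1 patients.

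The documents give no true DLT rate, so p is an assumption. At p = 0.30:
- the probabilities for k = 2, 3, 4 are 0.0900, 0.1260 and 0.1323, which sum to 0.348;
- the mean number treated after certainty is 3 × 0.0900 + 2 × 0.1260 + 1 × 0.1323 = 0.654.

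The chance of elimination after 5 patients is 1 − (1 − p)⁵ − 5p(1 − p)⁴.

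| p | eliminated after 5 | certain before patient 5 | mean treated after certainty |
|---|---|---|---|
| 0.15 | 0.165 | 0.110 | 0.19 |
| 0.30 | 0.472 | 0.348 | 0.65 |
| 0.40 | 0.663 | 0.525 | 1.04 |

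The means are per first cohort and assume that each DLT is known at once.

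**3. Allow for delay.** Protocol 4.6 defines "The safety outcomes within 7 days, which are categorized as dosage-limiting toxicities". The Protocol 4.3 table gives "Recruitment and follow-up 9 months". Spreading 60 patients evenly gives 9 × 365.25 / 12 / 60 = 4.57 days between patients. Simulating 200,000 or more cohorts with exponential gaps gives these means per first cohort:
- DLT onset uniform over 0–7 days: about 0.12, 0.43 and 0.69 at p = 0.15, 0.30 and 0.40.
- DLTs known only at day 7, p = 0.30: 0.27.
- Uniform onset plus an assumed adjudication delay, p = 0.30: 0.37 with 1 day and 0.29 with 3 days.
- Uniform onset, 3-day delay and gaps of 2.3 days, p = 0.30: 0.11.

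**4. Later cohorts.** From 1 DLT in 5, three more are needed to reach 4 in 10. Certainty before that cohort's last patient has probability p³ + 3p³(1 − p), which is 1.2% at p = 0.15 and 8.4% at p = 0.30. From 0 in 5 it needs four DLTs in four patients: p⁴, or 0.8% at p = 0.30. A dosage standing at 3 in 10 or 4 in 15 needs only two more and behaves like a first cohort. Its observed rate (0.30 or 0.27) is then already above the SAP's upper boundary of 0.179, so a further cohort there should be uncommon.

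**5. Does early closure alter a dose decision?** The final observed rate would be at least 2/5 = 0.40, 4/10 = 0.40, 5/15 = 0.33 or 6/20 = 0.30. All exceed 0.179 and all are E, so the remaining patients cannot alter the elimination.

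**The case against.** The strongest reply is that deciding by cohort is the SAP's stated design, that its boundaries are computed correctly, and that nothing obliges a site to complete a cohort after elimination is certain. Much of this stands. A reader might infer that the plan requires the cohort to be filled. The documents do not say so: step 2 governs the next cohort's dosage and is silent on the current one, and Protocol 5.4 could be read as stopping it. What remains is the absence of a stated trigger, with two texts that point different ways.

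A reader might also infer that the rule is breached whenever the posterior passes 0.95 mid-cohort, since 2/2, 2/3 and 2/4 give 0.9966, 0.9880 and 0.9734. That does not follow. One DLT in one patient gives 0.9775 and three in six give 0.988, yet eTable 1 does not eliminate for toxicity at 1 in 5 or 3 in 10. The argument is irreversibility under eTable 1, not the crossing itself.

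A larger size is also tempting. Dividing by the chance of elimination gives 0.654 / 0.472 = 1.39 patients at p = 0.30 and 1.037 / 0.663 = 1.56 at 0.40. Those figures are conditional on elimination and assume instant knowledge, at rates 2 to 2.7 times the 0.15 limit.

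DSMB review of SAEs and the Ethics Committee's power to suspend are real safeguards, and either could halt a cohort. Neither is tied to the DLT count. Finally, certainty depends on the CEC confirming the DLTs and on the patients being evaluable, so an unadjudicated event does not settle the matter.

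**Conclusion.** The point holds as a gap in the safety rule, not as an error in its arithmetic. Protocol 5.4 and SAP step 2 need reconciling on when elimination takes effect. Two confirmed DLTs among the first 2 to 4 evaluable patients at a dosage fix its elimination, and up to 3 further patients may then be treated there.

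The average effect is below one patient per first cohort in most of the cases examined. It reaches 1.04 only at an assumed rate of 0.40 with instant knowledge, and realistic delays reduce it without removing it. The size rests on the assumed true DLT rates, onset pattern, accrual and adjudication time. The boundaries rest on the assumed Beta(1,1) prior, which reproduces eTable 1. Because no threshold needs to move, this is a worthwhile and inexpensive improvement.

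**What to change.** Reconcile Protocol 5.4 with SAP step 2 by adding one statement to both:

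- The existing eTable 1 toxicity elimination count for the cohort in progress (2 for patients 1–5, 4 for 6–10, 5 for 11–15, 6 for 16–20) takes effect as soon as CEC-confirmed DLTs in evaluable patients reach it.
- Assignment to that dosage pauses while a potentially deciding DLT is adjudicated.
- The 0.95 cutoff is not applied after every patient.

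In Protocol 7.4, send suspected DLTs to the CEC and DSMB within the 24 hours already used for SAE reports. eTable 1 needs no new rows, and no threshold or elimination decision changes.

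**Cost.** One SAP sentence, the matching sentence in Protocol 5.4 and one reporting line. Some cohorts will close with fewer than 5 patients. An eliminated dosage then has fewer data, and its observed DLT rate is biased upward because the cohort closed on a DLT (2/2, 2/3 or 2/4). The SAP should say so where that estimate is reported or enters the isotonic fit. A pause for adjudication may briefly slow accrual.
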